are used for surgical or other reasons, please record them in detail.

- 4) Intraoperative anesthesia management: if the anesthetic effect of the local anesthesia group can not complete the operation, the anesthesiologist can decide to use the drug or change the general anesthesia and record it in detail. This study does not make any provision for this situation. The general anesthesia group adjusted the depth of general anesthesia according to the surgical stimulation. Blood pressure reduction base value 30% or systolic blood pressure less than 90 mmHg is hypotension, recommended for vasoactive drugs or liquid treatment, the anesthesiologist can be appropriate according to personal experience.
- 5) Postoperative analgesia: various analgesia methods can be used (intravenous, epidural, nerve block sustained or self-controlled analgesia, or combined with oral medication), but both groups avoid using any sedative.

Considering the actual situation and the particularity of geriatric anesthesia, it is estimated that there will be some differences in the implementation of anesthesia, puncture technique, and intraoperative management among the research centers and anesthesiologists. The scheme does not provide for these differences or differences.

8. Main indicators:

Incidence of delirium within 7 days after surgery (CAM)

9. Secondary indicators:

- 1) Delirium type, severity, duration (diagnosed by DRS-R-98 scale)
- 2) Postoperative pain score VAS pain score)
- 3) Other related complications and outcomes: related complications: pulmonary infection, myocardial infarction, renal failure,

gastrointestinal bleeding;

- 4) Hospitalization time
- 5) The mortality rate during hospitalization and 30 days after surgery
- 6) The total cost of hospitalization and anesthesia.
- 7) 6 months and 1-year follow-up: incidence, type, severity, the cognitive function of delirium (mini-mental state examination, MMSE), quality of life (The MOS 36-item Short-Form Health Survey, SF-36) Hospital Anxiety and depression scale, HADS mental state), mortality.

Description:

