| Alanine aminotransferase | * | * | * | * | * | * | * | * |
| Album | * | * | * | * | * | * | * | * |
| Urea nitrogen | * | * | * | * | * | * | * | * |
| Creatinine | * | * | * | * | * | * | * | * |
| PH | * | * | * | * | * | * | * | * |
| PO2 | * | * | * | * | * | * | * | * |
| PCO2 | * | * | * | * | * | * | * | * |
| HCO3 | * | * | * | * | * | * | * | * |
| Na | * | * | * | * | * | * | * | * |
| K | * | * | * | * | * | * | * | * |
| Cl | * | * | * | * | * | * | * | * |
| Delirium CAM or not | * | * | * | * | * | * | * | * |
| DRS-R-98 of type and severity of delirium | * | * | * | * | * | * | * | * |
| VAS pain score | * | * | * | * | * | * | * | * |

Table 2: Other data to be collected

| Period | Data | Method |
|---------------------------|--|--|
| Preoperative general data | Age, sex, address, type of fracture History, ASA rating Cognitive function (MMES) | Medical records MMSE |
| Intraoperative | Methods of operation, level of the surgeon, manner of anesthesia Anesthesiologist level, anesthetic substance, and dosage Low blood pressure | Review of medical records and anesthesia records |

| | | |
|------------------------------|---|--|
| | Duration of operation estimated blood loss | |
| Postoperative | Length of stay, hospitalization costs, anesthesia costs, adverse events, mortality during hospitalization,30-day mortality, withdrawal from the study | Telephone follow-up |
| 6 months and 12 months later | Whether delirium occurs, type and severity Mortality Quality of life, anxiety or depression | Quality of life scale SF-36, anxiety and depression scale (HADS) Review of patients' families |

11. Adverse event reports

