2.2 Objectives

This clinical trial is pragmatic, multicentre, prospective, parallel grouped, randomised controlled. The RAGA trial aims to determine whether different types of anaesthesia (regional anaesthesia vs general anaesthesia) given to older patients undergoing hip fracture surgery result in the equivalent incidence of postoperative delirium.

This will be met through meeting the following aims (as specified in the protocol):

- Aim 1: To assess whether there are differences in the incidence of postoperative delirium in different groups (by age, existing cognitive impairment, or preoperative delirium) between groups;

- Aim 2: To compare the subtypes, severity, and duration of postoperative delirium between the anaesthesia groups;
- Aim3: To describe the pain scores in the postoperative period either regional anaesthesia or general anaesthesia;
- Aim4: To compare the occurrence of non-delirium complications between the groups;
- Aim 5: Assessment of the length of hospital stay between groups;
- Aim 6: Assessment of the mortality during the hospital stay and the follow-up period after hospital admission between groups;
- Aim 7: Assessment of the cognitive and functional decline and quality of life on 30 days, 6 months, and 12 months after surgery between groups.
- Aim 8: To assess the cost-effectiveness of using regional anaesthesia compared to general anaesthesia in terms of total in-hospital costs and expenditure of anaesthesia.

3. Study Methods

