6.2 Baseline Characteristics

Categorical data will be summarised by frequencies and percentages. Continuous data will be summarised by the number of responses, mean and standard deviation if deemed to be normally distributed, and the number of responses, median and interquartile range or total range if data appear skewed. Tests of statistical significance will not be undertaken, nor confidence intervals presented ⁷.

7. Statistical Analysis

7.1 Primary outcome:

The primary outcome is the incidence of postoperative delirium during 7 postoperative days, diagnosed with the Confusion Assessment Method, and will be a categorical variable.

7.2 Secondary outcome measures are as follows:

- The subtype, severity, and duration of delirium in 7 days after the surgery, diagnosed with the Delirium Rating Scale-Revised-98 and confusion Assessment Method, subtypes and duration of delirium are categorical variables, and severity score is a continuous variable;
- Duration of delirium, measured by days from the onset of delirium symptom to the resolution of symptoms, which is a continuous variable;
- The intensity of postoperative pain, measured with acute pain score in 7 days after the surgery using Visual Analogue Scale (VAS), which is a continuous variable;
- The occurrence of non-delirium in-hospital complications within 30 days after surgery, including chest infection, myocardial infarction, renal failure, gastrointestinal ileus, which is a categorical variable;
- Length of hospital stay, measured by the sum of inpatient days from admission to discharge, which is a continuous variable;
- Mortality during the hospital stay and during the follow-up period after hospital admission, which is a categorical variable;
- Incidence of delirium in the clinic or at the residence on 30-day, 6 months, 12 months after surgery, diagnosed with CAM, which is a categorical variable;
- Cognitive and functional decline on 30-day, 6 months, 12 months after surgery, diagnosed with Mini-Mental State Examination (MMSE) and Hospital Anxiety and Depression Scale, which is a categorical variable;
- Quality of life on 30 days, 6 months, 12 months after surgery, using 36-Item Short Form questionnaire, which is a categorical variable;

- Economic parameters, including total cost in hospital and expenditure for anesthesia and resource using costs, including equipment and disposables required for each anesthetic technique, which are the continuous variables.

8. Analysis Methods

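### SAP 7.2 lists HADS as a measure of cognitive and functional decline and labels the MMSE/HADS and SF-36 outcomes categorical, with no cut-offs, no definition of decline and no analysis method

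*SAP*

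**What the plan says.** SAP section 2.2 sets Aim 7 as "Assessment of the cognitive and functional decline and quality of life on 30 days, 6 months, and 12 months after surgery between groups". Section 7.2 turns this into two secondary outcomes. Cognitive and functional decline is "diagnosed with Mini-Mental State Examination (MMSE) and Hospital Anxiety and Depression Scale, which is a categorical variable". Quality of life is measured "using 36-Item Short Form questionnaire, which is a categorical variable".

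The protocol allots the instruments differently. Section 9, item 7, gives MMSE for cognition ("the cognitive function of delirium (mini-mental state examination, MMSE") and, as a separate entry, "Hospital Anxiety and depression scale, HADS mental state". In section 10, Table 2 lists MMSE among the preoperative data, printed as "Cognitive function (MMES". Its row for 6 and 12 months names "Quality of life scale SF-36, anxiety and depression scale (HADS" and does not name MMSE.

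SAP section 8.2 gives methods for SO1 to SO5 only. By their content these are delirium frequency counts, delirium duration, pain, in-hospital complications and length of stay. Protocol section 12.4.2 asks that the effect of baseline on efficacy indicators be considered, and section 12.4.3 names covariance analysis for measurement data.

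**The concern.** The SAP puts an anxiety and depression scale under a heading about cognition and function, where the protocol keeps the constructs apart. It has no separate anxiety or depression outcome. Neither document describes MMSE or HADS as measuring function, so functional decline has no named measure.

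The two outcomes are also called categorical without categories. Two analysts following section 7.2 could build different endpoints, and cut-offs could be settled after the data are seen. If the label is followed, information in the scores is lost. At stake are the clarity and precision of the long-term secondary results on cognition, mood and quality of life. The primary outcome is not touched.

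**Working it through.** **1. Instruments, side by side.**

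| Instrument | Protocol section 9, item 7 | SAP 7.2 | Preoperative value in Table 2 | Named in 6/12-month row of Table 2 |
|---|---|---|---|---|
| MMSE | cognitive function | cognitive and functional decline, categorical | yes | no |
| HADS | mental state | cognitive and functional decline, categorical | not listed | yes |
| SF-36 | quality of life | quality of life, categorical | not listed | yes |

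The SAP also asks for all three at 30 days. Protocol section 9, item 7, and Table 2 place them at 6 and 12 months only.

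**2. Search for categories, a definition and a method.** SAP section 5 gives MMSE thresholds by education, but they define pre-existing dementia for a subgroup, not decline. No threshold for HADS or SF-36 appears anywhere. Section 8.2 names no method for these outcomes. Section 4.2 names a log-binomial model in general terms; that model needs a two-category outcome, and the SAP does not say that it applies here. In the same 7.2 list, DRS-R-98 severity and VAS pain, which are also scores, are continuous.

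**3. The plan's own figure.** The only sample size stated is for the primary outcome (SAP 3.3): 26% against 26% × 0.7 = 18.2%, two-sided 5%, power 80%. With unpooled variances, n = (1.960 + 0.842)² × (0.26 × 0.74 + 0.182 × 0.818) / 0.078² = 7.849 × 0.34128 / 0.006084 = 440.3, so 441 per group. It reproduces exactly. No figure is stated for MMSE, HADS or SF-36.

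**4. What a binary cut would cost (illustration).** Assume a normal score, a common standard deviation and 441 assessed per arm. The number assessed at follow-up is not given. The standardised difference detectable with 80% power on the score is (1.960 + 0.842) × √(2/441) = 0.189. If a share p of one arm falls below cut c, the information kept is φ(c)² / [p(1 − p)]. The other arm's share is Φ(c − 0.189).

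| p in one arm | Share in the other | Information kept | Patients needed, relative | Power |
|---|---|---|---|---|
| 50% | 42.5% | 0.3989² / 0.25 = 0.637 | 1.57 | 61% |
| 30% | 23.8% | 0.3477² / 0.21 = 0.576 | 1.74 | 55% |
| 20% | 15.1% | 0.2800² / 0.16 = 0.490 | 2.04 | 47% |
| 10% | 7.1% | 0.1755² / 0.09 = 0.342 | 2.92 | 34% |

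**5. What baseline adjustment could gain (MMSE only, illustration).** Residual variance is 1 − ρ², where ρ is the correlation of preoperative with follow-up MMSE. The documents give no ρ. For assumed values of 0.3, 0.5 and 0.7 the factor is 0.91, 0.75 and 0.51. Power for the same 0.189 difference rises from 80% to 83.6%, 89.9% and 97.5%.

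**The case against.** The strongest reply is that section 7.2 is loose drafting, not an analysis decision. The same list calls delirium duration categorical in one bullet and continuous in the next, and section 8.2 analyses it with a generalised linear model. The type labels are therefore weak evidence. The education-specific thresholds in section 5 also suggest a reason why raw MMSE might be categorised. Both points stand, and they are why the loss of information can only be illustrated.

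Four stronger readings are tempting, and the documents support none of them.

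- A reader might infer that anxiety or depression will be counted as cognitive decline. No composite or either/or rule is written. Two domains and two instruments share one bullet, so separate reporting remains possible, and SAP 2.2 says that its aims follow the protocol.
- A reader might infer that the SAP discards baselines which the trial holds. Only MMSE has a listed preoperative value. The SAP states no model from which it was dropped, and decline may itself mean change from that value.
- A reader might conclude that Aim 7 goes unanswered. A categorical comparison of randomised groups still answers it, with less precision, and the absence of HADS and SF-36 baselines does not bias it.
- A reader might take 64% as the information this plan keeps. That figure needs a normal score, two categories and a median cut, none of which the SAP states. Finer categories lose less, and a skewed or ceiling-limited MMSE would behave differently.

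What the reply does not remove is that the text contradicts the protocol on the role of HADS, and that its categorical outcomes cannot be derived as written.

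**Conclusion.** The point holds in this form: SAP 7.2 misplaces HADS relative to protocol section 9, names no measure of function, and labels the MMSE/HADS and SF-36 outcomes categorical without cut-offs, a definition of decline or a method. It affects secondary outcomes only, and the 441 per group stands.

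The possible loss of precision is material if the label is followed as a two-way split: 64% of the information kept at a median cut and 34% at a 10% cut, under normality. The gain from adjusting MMSE for its baseline depends entirely on the assumed correlation. This should be corrected, because the change is cheap and agrees with the protocol's own approach to baseline and measurement data.

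**What to change.** In SAP 7.2 and 8.2:

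- Make HADS a separate anxiety and depression outcome.
- Analyse follow-up MMSE as a score in a linear model adjusted for preoperative MMSE. Because MMSE may be skewed or reach its ceiling, add a robust or rank-based sensitivity analysis.
- Analyse HADS and SF-36 as scores, compared between groups at each visit without baseline adjustment, since no baseline is listed.
- Keep any categorical decline as a descriptive addition, with its cut-off and reference value written down in advance.
- Either tie functional decline to an instrument already collected or remove the word from this item and from Aim 7.

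In the protocol, reconcile Table 2 with section 9, item 7, on MMSE at 6 and 12 months. Settle also whether the 30-day assessment in the SAP is scheduled.

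The cost is mainly SAP wording, best done before unblinding. No new data are needed provided that MMSE is collected at follow-up as section 9 lists; Table 2 leaves that to be confirmed.

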8.1 Primary outcome

For the analysis of the primary outcome measure, the log binomial model will be used to generate relative risks (RR) along with 95% confidence intervals. Statistical significance of the treatment group variable will be determined through the examination of the associated chi-squared statistic.

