The incidence of delirium before surgery includes (delirium from admission to surgery). CAM scale is used for the diagnosis of delirium in the ward; the CAM-ICU scale is used to diagnose delirium in the intensive care unit, that is, CAM-ICU is used when the CAM is not available. When there is a contradiction between the diagnosis obtained by the scale and the psychiatrist's diagnosis, when there are still differences after consultation, the diagnosis of the psychiatrist shall prevail. To prevent missed diagnosis, we should communicate with the medical staff in the ward on time. After the patient is selected, the family member or escort staff should be informed. The researcher should be informed of the evaluation of delirium when any abnormal performance of the patient's mood, consciousness, cognition and so on is found. When postoperative delirium is found, the subject should communicate with the competent physician and decide on further diagnosis and treatment if the patient's performance was normal 7 d after the operation, the visit ended, while the patient with continuous delirium was followed up until normal or discharged. Delirium patients were assessed by delirium rating scale 98 revised (DRS-R-98) for type and severity of delirium. The patient's assessment form was used as evidence of postoperative delirium and the duration of delirium.

10. Data collection

Arrange post-operative delirium assessment and data collection by a fixed staff member who should not know about the study design and purpose to reduce the error in the study report, assess the presence, type, severity of postoperative delirium daily, patient medical records and nurse records are also used to determine whether delirium occurs for a total of 7 days after surgery (delirium was observed and discharged). The data collection table is shown in Table 1. Besides, the mortality, hospitalization time, and discharge department were recorded. Table 2 summarizes other data to be collected.

Table 1 Data collected daily. P: days after surgery

| Time points | Preoperative evaluation | P1 | P2 | P3 | P4 | P5 | P6 | P7 |
|---|-------------------------|----|----|----|----|----|----|----|
| Temperature | * | * | * | * | * | * | * | * |
| Blood pressure | * | * | * | * | * | * | * | * |
| Heart rate | * | * | * | * | * | * | * | * |
| Oxygen saturation | * | * | * | * | * | * | * | * |
| Hemoglobin | * | * | * | * | * | * | * | * |
| Alanine aminotransferase | * | * | * | * | * | * | * | * |

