12.4.2 Content of statistical analysis

The main analysis includes:

(1) Distribution of cases between the two groups: Comparing total abscission rate and abscission rate due to adverse events.

(2) Comparability analysis: Comparison of demographic data and other baseline indicators to measure comparability between the two groups.

(3) Compliance analysis: To compare whether the two groups of patients were using the test drugs on time and on time, and the drugs that were not banned in the unused regimen.

(4) Validity analysis: both PP and ITT analyzed the main efficacy indicators; since this study is a multicenter clinical trial, the effects of central effect and baseline on efficacy indicators should be considered.

The incidence of delirium was compared by chi-square test, chi-square test, CMH chi-square test, delirium exacerbation analysis, H analysis of data consistent with normal distribution; otherwise, H test, single-factor analysis of delirium aggravation, The data that do not conform to normal distribution are tested by rank sum test or Kruskal-Wallis test (H test).

(6) Safety analysis: First of all, according to the requirements of the correlation of adverse reactions, the list describes the adverse events and adverse reactions in the two groups (including the number of cases of various adverse events, the number of cases of "normally abnormal" before and after the test and the rate of variation). The adverse reactions were statistically analyzed by the chi-square test.

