12.4.3 Statistical analysis methodology

Metrological data: First, the normal test is carried out, and the methods of t-test, pairing t-test, variance analysis, covariance analysis are used for those that conform to a normal distribution, and rank-sum test, paired rank-sum test, H test and so on are used for the data that do not conform to normal distribution.

Numbering data: using calibration chi-square test, Fisher accurate test, etc.; grade data using Ridit analysis, CMH method.

(3) Multi-center analysis of comprehensive efficacy: counting data using CMH method; measurement data using covariance analysis.

All the statistical tests were bilateral, and the P-value was less than or equal to 0.05.

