4.2 Modeling Principles

Intervention groups will be compared using a log-binomial regression model.

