5.2 Secondary outcomes

Severity and Subtypes

The 13 items from Delirium Rating Scale-Revised-98 contribute to a severity score (items are scored zero to three, range from zero [no delirium] to 39 [maximum severity]) including two items which also define hyperactive (score ≥ 1 on motor agitation), hypoactive (score ≥ 1 on motor retardation), mixed motor (score ≥ 1 on both motor items) or no motor (score=0 on both motor items) subtypes of delirium.

Visual analogue scale (VAS)

Pain scores are measured using VAS (ranges from 0 [no pain] to 100 [worst pain], assessed daily, over the seven days and the highest pain score will be reported as continuous data. The first three days' VAS also will be analysed by comparison between groups.

30-day mortality is all-cause mortality during 30 days post-surgery.

Length of hospital stay is calculated from the first post-operative day to discharge.

Costs of the anaesthetic procedure include the expenditure of anaesthesia; anaesthetic drug, and labour cost.

Total in-hospital costs include the expenditure of anaesthesia, surgery, and hospitalisation.

5.3 Subgroups:

Pre-delirium is defined as whether patients had delirium before the intervention, using the Confusion Assessment Method on the day of admission.

Pre-existing dementia is defined by the Mini-Mental State Examination (MMSE) score with thresholds adjusted for educational levels.

- MMSE scores from 0 to 17 without educational experience/illiteracy;
- MMSE scores from 18 to 20 with an educational level less than primary education;
- MMSE scores from 21 to 22 with an educational level less than high school diploma;
- MMSE scores from 23 to 24 with an educational level less than a bachelor's degree.

Age is categorised by groups 65 to 80 years vs >80 years.

6. Trial Population

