8.2 Secondary outcomes (SO)

SO1: Frequency counts will be summarised by treatment group. RR and associated 95% CI will be calculated.

SO2: Duration of delirium will be summarised using basic descriptive statistics and analysed using generalised linear model (GLM) methods.

SO3: Acute pain score using VAS will be summarised using basic descriptive statistics and analysed using GLM methods.

SO4: Occurrence of non-delirium in-hospital complications within 30 days after surgery will be summarised by treatment group, but no relative effect will be calculated.

SO5: Length of hospital stay will be summarised using median and IQR and analysed using GLM methods.

9. Planned subgroup analyses

Interpretation of subgroup analysis will be treated with caution (output will be treated as exploratory rather than definitive⁸). Analysis will be limited to the primary outcome, which is the incidence of postoperative delirium during 7 postoperative days, and the following subgroups

- Age, as defined by 65-80, >80
- Preoperative dementia, those with vs those without
- Preoperative delirium, those with vs those without.

The effects of these subgroups will be examined by adding the subgroup by treatment group interaction parameters to the log-binomial model. Wald tests will determine statistical significance (p-values) of these interaction parameters. Differences between the treatment groups within subgroups will only be examined if the interaction parameter is shown to statistically important (p-value <0.05).

10. Definitions and Derived Variables

Abbreviations & Definitions	
Abbreviation/acronym	Meaning
BCTU	Birmingham Clinical Trials Unit
BP	Blood Pressure
CONSORT	Consolidated Standards of Reporting Trials
DMC	Data Monitoring
ITT	Intention to Treat
SAE	Serious Adverse Event
SAP	Statistical Analysis Plan
TSC	Trial Steering
POD	Postoperative Delirium
GA	General Anesthesia
RA	Regional Anesthesia
GLM	Generalised Linear Model
Term	Definition
International Standard Randomized Controlled Trial	A Clinical Trial Registry
Protocol	Document s details the rationale, objectives, design, methodology, and statistical considerations of the study
Randomisation	The process of assigning trial subjects to Intervention or control groups using an element of chance to determine the assignments in order to reduce bias.
Statistical Analysis Plan	Pre-specified statistical methodology documented for the trial, either at the protocol or in a separate document.

11. Software Details

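### SAP 8.1 names no covariate or centre term for the primary risk ratio; fixing an adjusted model in advance would gain precision at little cost

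*SAP*

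**What the plan says.** SAP 4.2 gives the general principle: "Intervention groups will be compared using a log-binomial regression model". SAP 8.1 applies it to the primary outcome: "the log binomial model will be used to generate relative risks (RR) along with 95% confidence intervals". It then tests the treatment variable by a chi-squared statistic. Neither section names a covariate or a centre term, or says that the model has none.

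Baseline factors enter the SAP's modelling only in section 9. There, age, dementia and preoperative delirium are examined by "adding the subgroup by treatment group interaction parameters to the log-binomial model", and the results are labelled exploratory.

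The protocol goes a little further. Section 12.4.2 notes that, because the trial is multicentre, "the effects of central effect and baseline on efficacy indicators should be considered". Section 12.4.3, on combining centres, specifies "counting data using CMH method". Both sections also list ordinary chi-square tests.

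The obvious covariates are already scheduled. Age and MMSE are in Table 2 of protocol section 10, and a preoperative CAM is in Table 1. Neither document mentions stratified randomisation (protocol 6, SAP 3.2).

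**The concern.** A primary model should be fixed before unblinding so that two analysts would fit the same one. SAP 8.1 does not achieve this. Its wording fits a treatment-only model and equally a model with covariates, and the interaction models in SAP 9 are built on the same undefined base.

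The likely default, an unadjusted risk ratio (RR), also gives up information. The protocol's background calls age a major risk factor for delirium. Its research questions and the SAP's Aim 1 single out age, cognitive impairment and preoperative delirium. Protocol section 7 expects practice to differ between centres. With no stratification stated, nothing in the described design limits chance imbalance in these factors.

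At stake are precision, robustness to imbalance, and freedom from a choice of covariates made after the data are seen. Validity of the test is not at stake.

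**Working it through.** **1. The plan's own figure.** Inputs from SAP 3.3: 26% under general anaesthesia, a 30% relative reduction (18.2%, RR 0.70), two-sided 5%, 80% power.

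- Unpooled: n = (1.960 + 0.842)² × (0.26×0.74 + 0.182×0.818) / 0.078² = 440.3, so 441 per group.
- Pooled variance under the null gives 444.
- Dropout: 882 / 0.90 = 980, rounded up to 1000. That leaves about 900 evaluable, 450 per arm.
- Unadjusted power (pooled formula) is 79.8% at 441 and 80.6% at 450 per arm.

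The 441 is reproduced.

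**2. Analytic gain.** If covariates and centre explain a share R² of outcome variance, the standard errors shrink by √(1−R²). R² is not in the documents; 0 to 0.20 is assumed. At 450 per arm:

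| Assumed R² | Power | CI for log RR narrower by |
|---|---|---|
| 0 | 80.6% | 0% |
| 0.05 | 82.6% | 2.5% |
| 0.10 | 84.5% | 5.1% |
| 0.20 | 88.5% | 10.6% |

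**3. Simulation.** 3000 trials per scenario, 450 per arm, simple 1:1 randomisation, unequal centre sizes, true RR 0.70. The assumed weak / moderate / strong inputs were:

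- preoperative delirium prevalence 5/10/15%, odds ratio 3/4.5/6;
- dementia (standing in for MMSE) prevalence 15/22/30%, odds ratio 2/2.5/3;
- age odds ratio 1.3/1.4/1.5 per SD;
- centre SD 0.3/0.5/0.7 on the logit scale.

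| Predictors | Power, 9 centres: unadjusted → adjusted Poisson | Power, 12 centres | Fall in variance of log RR |
|---|---|---|---|
| Weak | 79.8 → 81.2% | 79.0 → 81.5% | 3–4% |
| Moderate | 80.3 → 84.0% | 80.2 → 83.9% | 9% |
| Strong | 80.4 → 86.5% | 79.9 → 86.3% | 14–15% |

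The Monte Carlo half-width is about 1.4 points, and comparisons are paired on the same data. In patients, a variance fall v is worth 900/(1−v) − 900: about 28 at 3%, 89 at 9% and 147 at 14%.

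Standardised logistic regression did slightly better (81.4–81.5%, 84.0–84.3%, 87.2–87.4%). Centre alone, by Mantel-Haenszel, cut variance by 0–5%. A repeat with 1500 trials and nine centres gave 80.7 → 81.1%, 81.3 → 85.4% and 79.5 → 86.9%.

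**4. Type I error** (moderate and strong cases, half-width 0.8 points): unadjusted 4.6–5.7%, adjusted Poisson 5.0–5.3%, standardised logistic 5.1–5.7%. All are compatible with 5%.

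**5. Chance imbalance.** A 2-SD difference between arms in preoperative delirium is 2√(2p(1−p)/450): 2.9, 4.0 and 4.8 points for p = 5, 10 and 15%. It moves the unadjusted RR by about 3%, 5–6% and 7–8%, and the adjusted RR by about 0.5% or less.

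**6. Adding the covariates to the log-binomial itself.** In Python (statsmodels) the adjusted model failed to converge or gave fitted risks of 1 or more in 77–83%, 99% and 100% of trials (weak, moderate, strong). In R, the SAP's software, a start at the log mean failed in 44%, 95% and 100%, and the default start in at least 99%. The unadjusted log-binomial never failed.

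**7. Missing MMSE.** With 10% missing completely at random and nine centres, a complete-case adjusted model gave 77.6/80.4/83.6% power. Mean fill with a missing indicator gave 81.4/83.9/86.7%.

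**8. Two inputs to settle first.** Protocol section 9 (Description) counts preoperative delirium as "delirium from admission to surgery", whereas SAP 5.3 defines it "using the Confusion Assessment Method on the day of admission". SAP 3.2 randomises one day before surgery, so the protocol's window can run past randomisation. The protocol title page lists twelve hospitals; SAP 3.3 says nine.

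**The case against.** The strongest reply is that nothing is broken. Without stratified randomisation, centre need not be in the model; an unadjusted RR is a legitimate choice for a pragmatic trial, and its confidence interval already allows for chance imbalance. The protocol wording is only a prompt to consider, it sits in a loosely translated list beside plain chi-square tests, and it comes from a 2014 version, while the SAP cites a later published protocol. One sentence in 8.1 saying the model is unadjusted would close the gap. All of that is fair. It is why this is an improvement to make rather than an error, and why a stated, justified unadjusted analysis is acceptable.

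The gain also rests on assumed predictor strengths, and in the weak case it is only 1.4 to 2.5 power points. That stands too.

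Three technical objections carry less weight:

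- The main simulation used binary dementia, not an MMSE score. Replacing it with a noisy continuous MMSE kept nearly all the gain.
- Poisson and standardised logistic regression can target different RRs, conditional and marginal. The mean adjusted RR stayed at about 0.70 here, but the SAP should state its target.
- Failure of the adjusted log-binomial depends on the solver. That softens the claim for weak predictors with a good starting value, but not for moderate or strong ones.

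One practical point stands. Protocol Table 1 has a single undated preoperative column, so it must be confirmed that a CAM made before randomisation can be identified.

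**Conclusion.** The concern holds as a recommended change. The SAP leaves the covariate set of its primary model unstated and does not take up the protocol's wording on centre and baseline. The unadjusted test and the sample size are sound.

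Prespecified adjustment is worth about 1 to 6 power points at 450 per arm (variance of log RR down about 3% to 15%), with type I error held near 5%. If the covariates explain nothing, the cost is negligible: a separate simulation of standardised logistic regression gave a variance ratio of 1.01. Direction and validity are secure; the size depends on predictor strengths that the documents do not give, so confidence in the magnitude is medium.

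Adjustment does not settle whether delirium already present before surgery counts as a primary event. That is a separate question of endpoint definition.

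**What to change.** In SAP 8.1, state the primary RR as adjusted for centre, age, preoperative delirium (CAM, last assessment before randomisation) and baseline MMSE score. Estimate it by Poisson regression with robust standard errors. Standardised logistic regression is an acceptable alternative; name one, and say whether the target RR is conditional or marginal. Do not make a covariate-adjusted log-binomial the primary method. Report the unadjusted log-binomial RR alongside.

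Add two rules so that no randomised patient with an outcome is dropped, in keeping with SAP 4.6:

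- Set a missing baseline MMSE to the overall mean and include a missing indicator.
- Pool centres with fewer than 20 patients. At the planned average risk of 22.1%, the chance of no event is 0.779¹⁰ = 8% in a centre of 10 and 0.779²⁰ = 0.7% in a centre of 20.

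If the team prefers an unadjusted primary analysis, 8.1 should say so and give the reason. Either way, align protocol 12.4.2 and 12.4.3, and reconcile the definition of preoperative delirium and the number of centres between the two documents.

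The cost is SAP wording and a few lines of R. No new measurements are needed, provided the preoperative CAM can be dated. The downsides are a change of primary estimator, covariate and pooling rules that must be fixed before unblinding, and a gain of only 1–3 power points if the predictors prove weak.
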